3.5. Safety Endpoints

3.5.1. Adverse Events

An adverse event is considered a Treatment-Emergent Adverse Event (TEAE) if the event started during the effective duration of treatment. All events that start on or after the first dosing day and time/start time, if collected, but before the end of the study will be flagged as TEAEs. The algorithm will not consider any events that started prior to the first dose date.

3.5.2. Laboratory Data

Safety laboratory tests will be performed as described in the protocol. Baseline is defined as the last pre-dose measurement collected on Day -1.

To determine if there are any clinically significant laboratory abnormalities, the hematology, chemistry, urinalysis and coagulation tests will be assessed against the criteria specified in Clinical Data Interchange Standards Consortium (CDISC) standard. The assessment will not take into account whether each participant's baseline test result is within or outside the laboratory reference range for the particular laboratory parameter.

3.5.3. Vital Signs Data

Supine blood pressure (BP) and pulse rate (PR) will be taken at times detailed in the SoA given in the protocol. When triplicate BP and PR are required, the average of the triplicate BP and PR measurements collected prior to dosing on Day 1 will serve as baseline. Change from baseline in supine BP and PR will be determined.

PFIZER CONFIDENTIAL

3.5.4. ECG Results

Supine triplicate 12-lead ECGs will be obtained at each assessment time indicated in the SoA given in the protocol. For each ECG parameter, the average of the triplicate readings collected at each assessment time will be used to represent a single observation. Baseline will be defined as the last pre-dose recordings on Day 1. Change from baseline in QT interval, heart rate, QTcF interval, PR interval, and QRS interval will be determined.

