| Assessment of eligibility,
medical/medication history c           | X         | X                                     |                       |       |       |       |       |        |               |           |           |           |           |           |            |   |
| Physical exam and weight (plus height
at Screening, only) d       | X         | X                                     |                       |       |       |       |       |        | X             | X         | X         | X         | X         | X         | X          | X |
| Review alcohol/caffeine/tobacco, as
applicable                               | X         | X                                     |                       |       |       |       |       |        | X             | X         | X         | X         | X         | X         | X          | X |
| Review prior or concomitant
treatments, as applicable                        | X         | X                                     | →                     | →     | →     | →     | →     | →      | →             | →         | →         | →         | →         | →         | →          | X |
| Demography  | X         |                                       |                       |       |       |       |       |        |               |           |           |           |           |           |            |   |
| Review contraception use  | X         | X                                     |                       |       |       |       |       |        | X             | X         | X         | X         | X         | X         | X          | X |
| Serious and non-serious AEs
monitoring                                       | X         | X                                     | →                     | →     | →     | →     | →     | →      | →             | →         | →         | →         | →         | →         | →          | X |
| Injection site assessment e  |           |                                       | X                     | →     | X     |       |       |        |               |           |           |           |           |           |            |   |
| Supine 12-lead ECG (triplicate)   | X         |                                       | X f        |       | X     | X     |       | X      | X             |           |           | X         | X         |           |            | X |

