| Safety laboratory tests h   | X                 | X |                                    |       | X     | X     | X     |        | X             | X         | X         | X         | X         |           | X X        |
| CCI   |                   |   |                                    |       |       |       |       |        |               |           |           |           |           |           |            |
|  |                   |   |                                    |       |       |       |       |        |               |           |           |           |           |           |            |
| Blood Sample (s): serum ponsegromab (PK)   |                   |   | X i                     | X     | X     | X     | X     | X      | X             | X         | X         | X         | X         | X         | X X        |
| Urine drug test  | X                 | X |                                    |       |       |       |       |        |               |           |           |           |           |           |            |
| COVID-19 test(s) j  | X                 |   |                                    |       |       |       |       |        |               |           |           |           |           |           |            |

- Participants will admit to CRU at least 12 hours prior to dosing. Admission procedures to be conducted once, unless deemed necessary by investigator or sponsor.
- FU to approximately 18 weeks postdose planned; FU visits may be adjusted at investigator/sponsor discretion, including to monitor open AE, or based on emerging data (see [Section 4.4](#)).
- Medication history will be updated at each visit.
- Full PE at Screening or admission; at all other timepoints, limited PE performed for findings during previous exam or new/open AEs, at investigator discretion. PE may be conducted at final FU visit, at investigator discretion. Body weight to be measured at all indicated timepoints.
- Injection site assessment at predose (-30 min to 0 h), and 1 h (±10 min), 6 h (±0.5 h), 12 h (±1 h) and 24 h (±2 h) postdose. Additional assessments at investigator discretion and/or until any symptoms resolve. Additional requirements see [Section 8.2.2](#).
- Baseline ECGs should be triplicate collections at 60 min (±5 min) predose, 30 min (±5 min) predose, and 15 min (±5 min) predose (nine measurements in total). Additional requirements on ECGs see [Section 8.2.4](#).

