### **8.2.4. Electrocardiograms**

Standard 12-lead ECGs utilizing limb leads (with a 10 second rhythm strip) should be collected at times specified in the [SoA](#) section of this protocol using an ECG machine that automatically calculates the heart rate and measures PR, QT, and QTcF intervals and QRS complex. The timing of the PK samples should drive the timing of the ECGs. Note that ECGs do not need to be recorded at every time a PK sample is collected, but whenever an ECG is recorded, a PK sample should be collected at approximately the same time (preferably immediately after). Alternative lead placement methodology using torso leads (eg, Mason-Likar) should not be used given the potential risk of discrepancies with ECGs

PFIZER CONFIDENTIAL

acquired using standard limb lead placement. All scheduled ECGs should be performed after the participant has rested quietly for at least 5 minutes in a supine position.

TriPLICATE standard 12-lead ECGs will be obtained approximately within 5 minutes. The average of the triplicate ECG measurements collected prior to dosing on Day 1 will serve as each participant's baseline value.

To ensure safety of the participants, a qualified individual at the investigator site will make comparisons to baseline measurements. Additional ECG monitoring will occur if a) the mean value from the triplicate measurements for any postdose QTcF interval is increased by  $\geq 60$  ms from the baseline and is  $>450$  ms; or b) an absolute QT value is  $\geq 500$  ms for any scheduled ECG. If either of these conditions occurs, then a single ECG measurement must be repeated at least hourly until QTcF values from 2 successive ECGs fall below the threshold value that triggered the repeat measurement.

If a) a postdose QTcF interval remains  $\geq 60$  msec from the baseline and is  $>450$  msec; or b) an absolute QT value is  $\geq 500$  msec for any scheduled ECG for greater than 4 hours (or sooner, at the discretion of the investigator); or c) QTcF intervals get progressively longer, the participant should undergo continuous ECG monitoring. A cardiologist should be consulted if QTcF intervals do not return to less than the criteria listed above after 8 hours of monitoring (or sooner, at the discretion of the investigator).

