6.6.4. Electrocardiograms

Absolute values and changes from baseline in QT interval, heart rate, QTcF interval, PR interval, and QRS complex will be summarized descriptively by cohort and time. Tables will be paged by parameter. Baseline is as defined in [Section 3.5.4](#).

Maximum and/or minimum absolute values and changes from baseline for ECG endpoints (QTcF interval, PR interval and QRS complex) will also be summarized by cohort using

categories as defined in [Appendix 1](#). Numbers and percentages of participants meeting the categorical criteria will be provided. All planned and unplanned post-dose time points will be counted in these categorical summaries.

Listings of participants with any single post-dose value >500 msec will also be produced for QTcF.

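### SAP 3.5.4 appears to base the ECG baseline on only the last of three scheduled pre-dose triplicates, and SAP 6.6.4 omits the protocol's count of uncorrected QT above 500 msec

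*SAP*

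**What the plan says.** **Baseline, protocol.** The ECG row of the Schedule of Activities, "Supine 12-lead ECG (triplicate"), has a single pre-dose entry on Day 1. Its footnote expands that entry: "Baseline ECGs should be triplicate collections at 60 min", then at 30 minutes, then at "15 min (±5 min) predose (nine measurements in total"). Section 8.2.4 says the "average of the triplicate ECG measurements collected prior to dosing on Day 1 will serve as" each participant's baseline. Section 9.3.2.1 defines change in QTc against the average of the Day 1 pre-dose triplicate values. Neither section singles out one of the three sets.

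**Baseline, SAP.** Section 3.5.4 first reduces each time point to one value: "the average of the triplicate readings collected at each assessment time will be used to represent a single observation". It then states: "Baseline will be defined as the last pre-dose recordings on Day 1". Section 6.6.4 adopts this rule for the ECG tables: absolute values and changes are "summarized descriptively by cohort and time. Tables will be paged by parameter. Baseline is as defined in" Section 3.5.4. Section 2.1, where departures from the protocol belong, declares none.

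**Uncorrected QT.** Protocol 9.3.2.1 says the number of participants with uncorrected QT above 500 msec will be summarized. SAP 6.6.4 restricts its categorical summaries to QTcF, PR and QRS, and its listing of values above 500 msec to QTcF. SAP Appendix 1 has no row for uncorrected QT.

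**The concern.** Two programmers could derive different ECG baselines from the same data. The reading that SAP 3.5.4 most naturally supports does not use six of the nine scheduled baseline tracings, and nothing in the SAP explains why. A noisier baseline widens every ECG change-from-baseline summary. It also makes chance entries more likely in the QTcF category for increases above 30 and up to 60 msec. With 9 participants per cohort, one such entry prints as 1/9 = 11%.

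The QT count is a simpler matter. The protocol commits to an output that tables programmed from the SAP would not contain.

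**Working it through.** **Count of tracings.** 3 pre-dose times × 3 replicates = 9, which matches the protocol footnote. The last triplicate alone uses 3 and leaves 9 − 3 = 6 unused.

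**Which set the SAP means.** SAP 3.5.4 makes the triplicate mean at each assessment time one observation. With collections at 60, 30 and 15 minutes before dosing, the last one is the 15-minute set. SAP 3.5.3, just before it, sets the BP and pulse-rate baseline as the average of the Day 1 pre-dose triplicate. SAP 3.5.4 does not carry that wording over to ECG, which supports the last-set reading.

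**Effect on precision.** The documents give no QTcF variability, so these are assumptions:
- T is the within-participant SD of a triplicate mean.
- R is the correlation between pre-dose triplicate means, from 0 to 1.
- Post-dose triplicate means also have SD T and are independent of baseline.
- There is no drug effect.

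Baseline variance is T² with the last triplicate and T²(1 + 2R)/3 with the mean of three. Adding the post-dose variance T², the ratio of the SDs of change is

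√[2 / (1 + (1 + 2R)/3)],

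which does not depend on T:

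| R | 0 | 0.5 | 0.75 | 0.9 | 1 |
|---|---|---|---|---|---|
| SD ratio, last set / mean of three | 1.225 | 1.095 | 1.044 | 1.017 | 1.000 |

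**Effect on the category above 30 msec.** This is the probability that the largest of 7 post-dose changes exceeds 30 msec by chance, by numerical integration over the baseline error:

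| T (msec) | Last triplicate | Mean of three, R = 0 / 0.5 / 0.75 / 0.9 | Extra cases among 18, same R |
|---|---|---|---|
| 5.5 | 0.038% | 0.001 / 0.008 / 0.019 / 0.029% | at most 0.007 |
| 7.5 | 1.36% | 0.18 / 0.63 / 0.97 / 1.20% | 0.21 / 0.13 / 0.07 / 0.03 |
| 9.5 | 6.43% | 2.06 / 4.19 / 5.32 / 5.99% | 0.79 / 0.40 / 0.20 / 0.08 |

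Extra cases are 18 × the difference in probabilities. For example, at T = 9.5 and R = 0: 18 × (0.0643 − 0.0206) = 0.79. At R = 1 the difference is zero. A Monte Carlo check with 2 million draws at T = 7.5 and R = 0.5 gave 1.364% against 0.632%.

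The count of 7 post-dose ECGs comes from a schedule row that is partly broken in the text available. With 6, T = 7.5 gives 1.20% against 0.16 / 0.55 / 0.84 / 1.05%. The probability of an increase above 60 msec never exceeds 0.0027% (T = 9.5, last triplicate).

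**Uncorrected QT.** No arithmetic applies. SAP 6.6.4 keeps descriptive QT summaries by cohort and time, and SAP 5.2 includes the maximum, so an extreme mean QT would be visible. The number of participants above 500 msec would not be tabulated: it is not in 6.6.4 or Appendix 1, and the reference in 6.6 to standard CDISC tables does not name it.

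**The case against.** The strongest reply is that the baseline issue is an ambiguity, not a departure. No protocol passage says outright that all nine readings are averaged. Section 8.2.4 says that triplicate "standard 12-lead ECGs will be obtained approximately within 5 minutes", which describes one set and not three spread over 45 minutes. If the protocol leaves the set open, SAP 3.5.4 may simply settle it, and SAP 2.1 then has nothing to declare. The SAP wording can also be read as the whole Day 1 block, because the schedule row has one Day 1 entry. SAP 3.4, the general baseline rule, supports that reading: it refers to Day 1 pre-dose values in the plural and applies the idea of a last measurement only to Day −1. Both documents also allow the SAP to modify the protocol and require an amendment only for major changes to the primary endpoints.

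On size, sets taken minutes apart in a resting person may be highly correlated, and at R of 0.75 to 0.9 the loss in SD is only 4.4% to 1.7%.

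Much of this stands. The protocol is loose, the block reading is possible, and the R = 0 figures are an upper bound. But SAP 3.4 does not say how the three sets are combined, so the SAP still lacks a definite rule, and the reading it most naturally invites uses the least data.

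On the QT count, the reply is that the protocol still states it and at most about 18 participants are involved. That limits its weight but does not put the count in the SAP.

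**Conclusion.** Both parts hold, at minor severity. The baseline part rests on the most natural reading of SAP 3.5.4, not the only one. If that reading applies, the loss in precision runs from 22% of the SD of change down to nothing, depending on a correlation the documents do not give. The expected number of spurious entries above 30 msec stays below one among 18 participants in every case examined. The QTcF category above 60 msec and the primary PK results are not materially affected, and the absolute QTcF categories do not use baseline. The missing QT count follows directly from comparing Protocol 9.3.2.1 with SAP 6.6.4 and Appendix 1, and needs no assumption.

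**What to change.** 1. In SAP 3.5.4, define baseline for each ECG parameter as the mean of all available Day 1 pre-dose triplicate means (nominally 60, 30 and 15 minutes before dosing). If the sponsor intends the last triplicate only, name that set in 3.5.4 and state and justify the choice in SAP 2.1.
2. In SAP 6.6.4, add the number of participants with uncorrected QT above 500 msec, by cohort.

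The cost is one sentence, a small change to the baseline derivation and one extra count. The tracings are already scheduled, so no new data and no protocol amendment are needed.

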4. ANALYSIS SETS (POPULATIONS FOR ANALYSIS)

For purposes of analysis, the following analysis sets are defined:

Participant Analysis Set	Description	Applicable Analysis (for additional information refer to section 6)
Enrolled	“Enrolled” means a participant’s agreement to participate in a clinical study following completion of the informed consent process and screening. Potential participants who are screened for the purpose of determining eligibility for the study, but do not participate in the study, are not considered enrolled, unless otherwise specified by the protocol. A participant will be considered enrolled if the informed consent is not withdrawn prior to participating in any study activity after screening.	
Safety Analysis Set	All enrolled participants who receive a dose of ponsegromab. Participants will be analyzed according to the product they actually received.	Secondary endpoints (section 6.2)
PK Concentration Analysis Set	All enrolled participants who receive a dose of ponsegromab and in whom at least 1 serum concentration value is reported.	Primary endpoints (section 6.1)
PK Parameter Analysis Set	All enrolled participants who receive a dose of ponsegromab and who have at least 1 of the serum PK parameters of interest calculated.	Primary endpoints (section 6.1) CCI
[REDACTED]	[REDACTED]	[REDACTED]

Participant Analysis Set	Description	Applicable Analysis (for additional information refer to section 6)
CCI		

5. GENERAL METHODOLOGY AND CONVENTIONS

5.1. Hypotheses and Decision Rules

There are no statistical hypotheses for this study.

5.2. General Methods

All data will be descriptively summarized.

Binary and categorical variables will be presented using summary statistics: number of observations and percentages.

Continuous variables will be presented using summary statistics: number of observations, arithmetic mean, standard deviation (SD), coefficient of variation (cv%), median, minimum, maximum, geometric mean and geometric cv%.

5.3. Methods to Manage Missing Data

5.3.1. Safety Data

For the analysis of safety endpoints, the sponsor data standard rules for imputation will be applied.

5.3.2. Pharmacokinetic CCI Data

Concentrations Below the Limit of Quantification

In all PK data presentations (except listings), concentrations below the limit of quantification (BLQ) will be set to zero.

In all CCI data presentations (except listings), concentrations below the limit of quantification (BLQ) will be set to the LLQ.

In listings, BLQ values will be reported as “<LLQ”, where LLQ will be replaced with the value for the lower limit of quantification (LLQ).

Deviations, Missing Concentrations and Anomalous Values

For PK **CCI** summary tables, plots of mean profiles and plots of median profiles, summary statistics will be calculated setting concentrations to missing if one of the following cases is true:

1. A concentration has been collected as ND (i.e., not done) or NS (i.e., no sample);
2. A deviation in sampling time is of sufficient concern or a concentration has been flagged anomalous by the pharmacokineticist.

Note that summary statistics will not be presented at a particular time point if more than 50% of the data are missing.

Pharmacokinetic **CCI Parameters**

Actual PK **CCI** sampling times will be used in the derivation of PK **CCI** parameters.

If a PK **CCI** parameter cannot be derived from a participant's concentration data, the parameter will be coded as NC (i.e., not calculated). (Note that NC values will not be generated beyond the day that a participant discontinues.)

In summary tables, statistics will be calculated by setting NC values to missing; and statistics will be presented for a particular dose with ≥ 3 evaluable measurements.

If an individual participant has a known biased estimate of a PK **CCI** parameter (e.g., due to an unexpected event such as vomiting before all the compound is adequately absorbed in the body), this will be footnoted in summary tables and will not be included in the calculation of summary statistics. For PK parameter calculations, the sponsor standard rules will be applied.

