3. ENDPOINTS AND BASELINE VARIABLES: DEFINITIONS AND CONVENTIONS

As listed in [Section 2.2](#) the primary and the other endpoints are related to ponsegromab serum PK and are described herein.

Samples for the PK analysis of ponsegrumab will be taken according to the schedule of activities (SoA) given in the protocol.

PFIZER CONFIDENTIAL

Ponsegromab serum PK parameters (unbound and total) will be derived (if data permit) from the concentration-time profiles using standard non-compartmental methods as detailed in Table 2. Actual PK sampling times will be used in the derivation of ponsegromab serum PK parameters (unbound and total). In the case that actual PK sampling times are not available, nominal PK sampling times will be used.

Table 2. Ponsegromab Serum PK Parameters (unbound and total)

Parameter	Definition	Method of Determination
C_{\max}	Maximum serum concentration	Observed directly from data
CC1		
T_{\max}	Time for C_{\max}	Observed directly from data as time of first occurrence
$t_{1/2}^a$	Terminal half-life	$\log_e(2)/k_{el}$, where k_{el} is the terminal phase rate constant calculated by a linear regression of the log-linear concentration-time curve
AUC_{last}	Area under the serum concentration-time profile from time zero to the time of the last quantifiable concentration (C_{last})	Linear/Log trapezoidal method
CC1		
AUC_{inf}^a	Area under the serum concentration-time profile from time zero extrapolated to infinite time	$AUC_{\text{last}} + (C_{\text{last}}/k_{el})$, where C_{last} is the predicted serum concentration at the last quantifiable time point estimated from the log-linear regression analysis
CC1		

a. As data permit.

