3.1. Primary Endpoint(s)

The primary endpoints are below ponsegromab serum PK parameters (unbound and total):

- AUC_{inf} , AUC_{last} , C_{\max} , T_{\max} , and $t_{1/2}$.

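### Does SAP 5.3.2 need a rule for an AUClast cut short by early withdrawal?

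*SAP*

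**What the plan says.** SAP 3.1 names AUClast as one of five primary PK parameters, for unbound and total drug. SAP Table 2 defines it as "Area under the serum concentration-time profile from time zero to the time of the last quantifiable concentration", with no fixed end time and no minimum coverage. SAP 4 admits to the PK Parameter Analysis Set dosed participants "who have at least 1 of the serum PK parameters of interest calculated".

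SAP 5.3.2 gives two routes by which a parameter value leaves a summary:

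- **Not calculable.** "In summary tables, statistics will be calculated by setting NC values to missing". This applies when the parameter cannot be derived.
- **Known to be biased.** "If an individual participant has a known biased estimate of a PK" parameter, "this will be footnoted in summary tables and will not be included in the calculation of summary statistics". The single illustration is vomiting before absorption is complete, and it is introduced as an example, not as a full list.

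The same paragraph ends: "For PK parameter calculations, the sponsor standard rules will be applied". Those rules are not reproduced.

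SAP 6.1 lists the parameters and summarises them by cohort. It also lists every concentration with its actual time and plots individual profiles. Protocol 9.5 plans 9 participants per cohort to obtain about 8 evaluable.

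**The concern.** A participant who leaves on Day 15 with drug still quantifiable has an AUClast covering two weeks, while a completer's covers up to 15 weeks. Averaging the two mixes different quantities. The value can be calculated, so the not-calculable route does not remove it. Whether the bias route does is left open, and two analysts could answer differently.

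The stake is the summary of a primary endpoint in cohorts of nine. Protocol 4.2 wants the PK parameters to allow comparison among ethnic populations. Enrolling nine to get eight allows for one incomplete participant per cohort. The study is open-label with data reviews permitted (SAP 7.1), so a choice made after seeing the values could look selective. Protocol 9.3 also expects the SAP to describe how missing, unused and spurious data are handled.

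**Working it through.** **What the text implies.** An area ending at an early last sample meets the Table 2 definition. It is not NC, and one calculated parameter puts the participant in the analysis set. Unless someone judges it biased, it is summarised. Set membership alone does not decide this, because 5.3.2 excludes value by value.

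**The plan's own figures.** 2 × 9 = 18 enrolled and 2 × 8 = 16 evaluable, an allowance of 1/9 = 11% per cohort. No dropout rate, PK variance or half-life is visible.

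**Size if one truncated value is kept.** Assumed, not in the documents: one-compartment kinetics with first-order absorption, half-life 10, 14, 21 or 28 days, ka 0.2 or 0.4 per day, drug quantifiable throughout. AUClast is computed by the linear/log trapezoidal rule (SAP Table 2) at the sampling times in the Schedule of Activities.

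- f = AUC to the last sample ÷ AUC to Day 106, same participant.
- Change in the geometric mean with one such value of nine = f^(1/9) − 1.
- Example (half-life 21 days, ka 0.4, Day 15): f = 0.323, and 0.323^(1/9) = exp(−1.130/9) = 0.882, or −11.8%.

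| Last sample | f, example kinetics | Change, example | Range of change over the grid |
|---|---|---|---|
| Day 8 | 0.144 | −19.4% | −14 to −24% |
| Day 10 | 0.198 | −16.5% | −11 to −21% |
| Day 15 | 0.323 | −11.8% | −7 to −16% |
| Day 29 | 0.586 | −5.8% | −2 to −8% |
| Day 50 | 0.811 | −2.3% | −0.5 to −4% |
| Day 71 | 0.923 | −0.9% | −0.1 to −1.5% |

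If the leaver is replaced and both values are summarised, the exponent is 1/10. For Day 15, 0.323^(1/10) − 1 = −10.7%.

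**Yardstick.** With an assumed geometric CV of 30%, s = √ln(1.09) = 0.294. One standard error of the log mean is 0.294/3 = 0.098, about 9 to 10%. In the example, exits up to Day 15 exceed it and Day 29 does not. At a CV of 40% the standard error is √ln(1.16)/3 = 0.128 on the log scale. The Day 15 shift (1.130/9 = 0.126) is then just inside it.

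**Would it be noticed?** Place the leaver at f times the geometric mean of eight complete profiles with log SD s. The log variance of the nine is [7s² + (8/9)(ln f)²]/8.

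- Day 15: (7 × 0.0862 + 0.889 × 1.277)/8 = 0.217, a geometric CV of √(e^0.217 − 1) = 49%.
- Day 10: about 67%.
- Day 29: 33.6%, little different from 30%.

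In a simulation of nine log-normal values under the same assumptions, the leaver is the cohort minimum in about 98% of samples for Day 15, nearly all for Day 10, and about 63% for Day 29. The median moves by about −4% in each case. So exits that move the geometric mean by more than a standard error also stand out in the minimum and geometric CV. SAP 5.2 provides for both: "Continuous variables will be presented using summary statistics" is followed by a list that includes them.

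**The case for a change.** The strongest opposing case is that pre-specification exists for this situation. AUClast is primary and the study's main output is its descriptive summaries. One sentence would remove any discretion over a value already seen. The sponsor rules are cited for calculating parameters, which is not plainly the same as deciding what enters a summary. AUCinf is only a partial safeguard. A Day 10 or Day 15 leaver may have too few post-peak samples for a terminal slope, so AUCinf may be missing while AUClast is kept, and the two primary areas would then rest on different participants.

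Most of this stands as description. The gap exists, and the differing-participants point is fair, although the number of observations behind each summary would show it. What does not follow is that the plan gives a wrong answer. The remedy would be content with either inclusion or exclusion, or with a citation of the sponsor rule, so it asks for wording and does not offer a better method.

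Nor can it be said that a kept value would carry no mark in the summary table. SAP Table 3 is partly redacted and AUClast is not visible in it, so its notes cannot be checked. The last sampling day can in any case be read from the concentration listing.

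**Conclusion.** This is a gap that analysts can fill sensibly. The definition of AUClast gives a default (keep the value), the known-bias clause leaves room for a documented exception, and the sponsor rules may already decide it. Kept or excluded, the participant's value, sampling times and profile are reported.

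The effect is confined to withdrawal up to about Day 29: roughly 7 to 16% on the cohort geometric mean at Day 15, up to 24% if nothing is sampled after Day 8, and 2 to 8% at Day 29. Participants stay in the unit through Day 8 (protocol 4.1), and an early-discontinuation visit is sought (protocol 7.2).

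These figures rest on assumed half-life, absorption and CV. They ignore the target-mediated disposition noted in protocol 2.1; a faster late fall in unbound drug would make the shift smaller. SAP 5.1 states no hypotheses, so no formal conclusion can turn on the choice. A clarifying sentence, or a note of the leaver's last sampling day, would be reasonable if the SAP were opened for another reason. The point does not call for a change by itself.
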